9.2.3 Site Performing Archival Tissue Studies

9.3 Circulating tumor DNA (ctDNA)

Blood will be collected at baseline, restaging visits and at time of progression for evaluation of circulating tumor DNA (ctDNA). The banked samples will be used to analyze DNA, RNA and protein in future studies.

9.3.1 Collection of ctDNA specimen(s)

One 10 ml of whole blood will be collected in Streck Tubes. The blood sample will be collected and processed at baseline, restaging visits and time of progression for evaluation of ctDNA. Fill the Streck tube completely and immediately mix by gentle inversion 8 to 10 times. Inadequate or delayed mixing may result in accurate results. The banked samples will be used to analyze DNA, RNA and protein in future studies.

9.3.2 Handling and shipping of ctDNA specimens

One 10 ml Streck tube will be collected and processed at baseline, restaging visits and at time of progression for evaluation of ctDNA. Fill the Streck tube completely and immediately mix by gentle inversion 8 to 10 times. Inadequate or delayed mixing may result in accurate results. Ship within 24 hours of collection at ambient temperature overnight to:

Email the blood bank [REDACTED] and the current Dana-Farber CRC with the sample information and tracking information the day before shipping specimens.

Tube precautions:

- If samples cannot be shipped within 24 hours of collection, contact DFCI. DO NOT FREEZE OR REFRIGERATE TUBES as this could result in ctDNA breakage. Blood collected in the Streck tube can be stored for 14 days between 6-37 degrees Celsius.
- Do not use tubes after expiration date.
- Fill the tube completely; overfilling or underfilling of tubes will result in an incorrect blood-to-additive ratio and may lead to incorrect analytical results.

Shipping Note: Streck tube samples are sent ambient. Frozen and ambient specimens obtained and shipped on the same day to the DFCI blood bank (e.g., Study Biopsy Specimens, Streck Tubes) may be placed in a combination shipping box which contains separate compartments for frozen and ambient samples. If a combination shipping box is not available, two shipping boxes should be used.

Blood in these tubes will be processed for collection of plasma (for ctDNA) See

Appendix B for additional instructions on use of Streck tubes.

9.4 Collection of Plasma Samples for Exploratory Biomarker Evaluations

EDTA-anticoagulated plasma samples will be collected and analysis may be performed on biomarkers that may play a role in the LY2835219 mechanism of action. The evaluation of these samples may involve analysis of DNA, RNA, and proteins (including any of these components derived from exosomes) to investigate their association with observed clinical outcomes to study drug.

9.4.1 Handling and shipping of plasma specimens:

One 10 mL purple top EDTA tube should be collected at C1D1, C1D15, C2D1, C3D1 and at time of progression. These samples should be sent to:

Once collected, the tube should be centrifuged, and the plasma separated into 2 aliquots and frozen in the Clinical Research Laboratory.

9.5 Germline DNA

The objective for collecting germline DNA is to perform germline exome sequencing as a control for the paired tumor biopsies.

9.5.1 Handling and shipping of plasma specimens:

One 10 ml Streck tube will be collected and processed at baseline for germline DNA. Fill the Streck tube completely and immediately mix by gentle inversion 8 to 10 times. Inadequate or delayed mixing may result in accurate results. Ship within 24 hours of collection at ambient temperature overnight to:

Email the blood bank  the current Dana-Farber CRC with the sample information and tracking information the day before shipping specimens.

Tube precautions:

- If samples cannot be shipped within 24 hours of collection, contact DFCI. DO NOT FREEZE OR REFRIGERATE TUBES as this could result in ctDNA breakage. Blood collected in the Streck tube can be stored for 14 days between 6-37 degrees Celsius.
- Do not use tubes after expiration date.
- Fill the tube completely; overfilling or underfilling of tubes will result in an incorrect blood-to-additive ratio and may lead to incorrect analytical results.

Shipping Note: Streck tube samples are sent ambient. Frozen and ambient specimens obtained and shipped on the same day to the DFCI blood bank (e.g., Study Biopsy Specimens, Streck Tubes) may be placed in a combination shipping box which contains separate compartments for frozen and ambient samples. If a combination shipping box is not available, two shipping boxes should be used.

Blood in these tubes will be processed for collection of the buffy coat for germline DNA. See Appendix B for additional instructions on use of Streck tubes.

9.6 PBMCs

As PBMC collections were added after the study began enrolling, collections will begin with the first patient enrolled after the activation of DFCI Amendment #6.

9.6.1 Handling and shipping of PBMC specimens:

Five 10 ml EDTA tubes will be collected and processed at baseline, C2D1, C3D1, and progression for PBMCs. Fill the tubes completely and deliver to the Center for Immuno-Oncology Lab within 3-4 hours of draw at the following address:

The CIO lab staff will send reminders each week; however, please notify the lab of any planned draws so that they can staff appropriately.

9.6.2 Potential Testing: Flow Cytometry

PBMCs will be generated as described in the appendix, and used to assess immune cell populations.

Surface staining with a panel of antibodies and flow cytometry on PBMCs will then be performed as described in Appendices. The following antibodies will be used on all specimens: (core set) CD8, PD-1, PD-L1, PD-L2.

A selection of the following antibodies may also be used, and additional antibodies may be used

as well, as deemed appropriate and informative based on the state of the immune profiling literature at the time of correlative science performance: CD4, FOXP3, CD127.

9.6.3 Site Performing Correlatives:

DFCI CIO

9.7 **Analysis of tissue biopsy specimens obtained at baseline and at C2D1**

9.7.1 Guidelines for Tissue Acquisition and Biopsies of Metastatic Lesions

9.7.1.1 Collection of Specimen(s)

Tissue specimens will be collected from recurrent or metastatic lesions using standard institutional procedures. The amount of tissue collected will follow the guidelines listed below. If a participant has more than one site of disease, only one site needs to be biopsied in order to go on to the study and the site is left to the discretion of the patient and their treating physician. Core biopsies are preferred over fine needle aspirates when both are technically feasible. However, fine needle aspirates are acceptable and may be used for the baseline tissue sample. Participants who undergo a research biopsy procedure for the purpose of this protocol, and in whom inadequate tissue is obtained, are still eligible and are not required to undergo a repeat biopsy in order to enter the study. Research biopsies can be waived, with PI approval, in participants who do not have easily accessible disease.

For the baseline biopsy, ideally five core biopsies will be obtained and processed as follows:

- First core will be placed in 10% neutral buffered formalin and then made into a formalin fixed paraffin embedded (FFPE) block.
- Second core will be frozen in OCT
- Third core will be placed in 10% neutral buffered formalin and then made into an FFPE block.**
- Fourth core will be frozen in OCT**
- Fifth core will be placed in DMEM

**If a biopsy yields less than five cores, the PI may opt to have the 3rd or 4th core placed in DMEM to send to the lab of [name]. This can be discussed with [name] in advance of the procedure.

For the C2 biopsy, ideally five core biopsies will be obtained and processed as follows:

- First core will be placed in 10% neutral buffered formalin and then made into a formalin fixed paraffin embedded (FFPE) block.
- Second core will be frozen in OCT
- Third core will be placed in 10% neutral buffered formalin and then made into an FFPE block.
- Fourth core will be frozen in OCT

- Fifth core will be frozen in OCT

Guidelines for biopsy from various metastatic sites can be found below.

Breast: A goal of 3-6 core biopsy specimens will be obtained using standard institutional guidelines for a diagnostic core biopsy of a breast mass.

Skin/chest wall: A goal of 3 x 4-mm punch biopsies will be obtained.

Lymph node: A goal of 3-6 core biopsy specimens will be obtained using an 18-gauge needle.

Liver: A goal of 3-6 core biopsy specimens will be obtained using an 18-gauge needle.

Lung: Because of the risk of pneumothorax associated with core needle biopsies of lung nodules, no core biopsies of lung nodules will be performed on this protocol, unless they are clinically indicated.

Bone: Because the yield of malignant tissue from bone biopsies tends to be relatively low, if a participant has another accessible site of disease (i.e. skin, lymph node, liver), that site should be biopsied preferentially. If bone is the only biopsy-accessible site, then a goal of 3-6 core biopsy specimens will be obtained using an 11-13 gauge needle.

Pleural Fluid: A goal of 500 cc of pleural fluid will be obtained with a standard thoracentesis procedure, with or without image guidance, according to the clinical judgment of the treating physician and clinician performing the procedure. Less than the goal amount is acceptable, and should be based upon the clinical judgment of the Investigator and the clinician performing the procedure. If more than the goal amount of fluid is obtained, then the entire specimen (with the exception of what is needed for clinical purposes, if applicable) will be stored in the tissue bank.

Ascites fluid: A goal of 500 cc of ascites fluid will be obtained with a standard paracentesis procedure, with or without image guidance, according to the clinical judgment of the treating physician and clinician performing the procedure. Less than the goal amount is acceptable, and should be based upon the clinical judgment of the Investigator and the clinician performing the procedure. If more than the goal amount of fluid is obtained, then the entire specimen (with the exception of what is needed for clinical purposes, if applicable) will be stored in the tissue bank.

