2.4 Correlative Studies Background

In this study, correlative scientific aims will be addressed by performing analysis of both archival patient specimens and specimens obtained during the course of the study. The overarching goal of these studies is to explore possible predictors of response to abemaciclib amongst RB-positive TNBC's. Furthermore, studies will seek evidence of a pharmacodynamic response to abemaciclib therapy (through a tumor biopsy obtained on study) to determine if this correlates with response to therapy.

The main candidate biomarker of tumor sensitivity to CDK4/6 inhibitors is the presence of intact, functional Rb [6]. At the time of screening patients for eligibility, therefore, we will perform immunohistochemistry to identify RB status on archival tumor tissue. Only patients that are RB-positive (greater than 50% of tumor cells staining positive) will be eligible for the study.

Other than RB, there are no validated biomarkers for predicting response/resistance to CDK4/6 inhibitors in breast cancer. Candidate markers of response include amplification of cyclin D1 and loss of the CDK4/6 inhibitor p16 [5], which are thought to render tumors more dependent on the CDK4/6 pathway. Conversely, possible predictors of resistance include amplification of cyclin E1/E2, overexpression of cyclin E, mutations in TP53, and heightened activity of phosphoinositide-dependent kinase 1. Finally, a failure of CDK4/6 inhibition to adequately achieve suppression of RB-phosphorylation, even in the presence of intact RB, is also predicted to be associated with a lack of response to therapy.

In this study, patients with biopsy-accessible disease will be required to undergo tumor biopsy prior to initiating therapy. In addition, patients will undergo a second biopsy after completion of 1 cycle (28 days) of abemaciclib therapy. Analysis of pre-treatment biopsies (or archival tissue when pre-treatment biopsies are not available) will be performed to determine correlations with the predictive biomarkers listed above (and others) and response. Comparison of RB phosphorylation between baseline and C2D1 biopsies will be used to seek evidence of pharmacodynamic effect and explore its association with response. We will also perform exploratory genomic studies (whole exome sequencing) on the tumor tissue, as well as studies on fresh tumor tissue obtained at baseline aimed at determining therapeutic combinations that enhance the effects of CDK4/6 inhibitors in TNBC.

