- 3.1.9 The patient has an Eastern Cooperative Oncology Group (ECOG) performance status 0-1 (ECOG scale provided as Appendix A)
- 3.1.10 Patients must have normal organ and marrow function as defined below:
- Absolute neutrophil count $\geq 1500/\text{mm}^3$
 - Platelets $\geq 100,000/\text{mm}^3$
 - Hemoglobin ≥ 8 g/dL
- Note:* Patients may receive erythrocyte transfusions to achieve this hemoglobin level at the discretion of the investigator. Initial treatment must not begin earlier than the day the after the erythrocyte infusion
- Total Bilirubin ≤ 1.5 x the upper limit of normal (ULN) or ≤ 2.0 x the upper limit of normal (ULN) in patients with documented Gilbert's syndrome.
 - Serum creatinine ≤ 1.5 mg/dL OR calculated GFR ≥ 60 mL/min
 - Alanine aminotransferase (ALT) and aspartate aminotransferase (AST) ≤ 3 times the upper limit of normal. For patients with documented liver metastases, AST/ALT ≤ 5.0 times the upper limit of normal.
- 3.1.11 Female subjects of childbearing potential must have a negative serum pregnancy test at screening. Women of childbearing potential are defined as those who have not been surgically sterilized and have had a menstrual period in the past year

- 3.1.12 The patient must be ≥ 18 years old
- 3.1.13 Capable of understanding and complying with the protocol and has signed the informed consent document.
- 3.1.14 Able to swallow study drug.
- 3.1.15 Sexually active patients (male and female) must use medically acceptable methods of contraception during the course of the study and for 3 months after completion of study treatment. If a woman becomes pregnant or suspects she is pregnant while participating in this study, she should inform her treating physician immediately. While on the study and for 3 months after final drug administration, women may not breast-feed.
- 3.1.16 Confirmed availability of formalin-fixed, paraffin-embedded (FFPE) tumor tissue
- 3.1.17 Patients with tumor that is felt to be accessible to biopsy must be willing to provide tissue from a newly obtained core biopsy of a tumor lesion at baseline. Biopsies will be obtained up to 1 week (7 days) prior to initiation of treatment on Cycle 1, Day 1. Patients who undergo an attempted research biopsy procedure for the purpose of this protocol, and in whom inadequate tissue is obtained, are not required to undergo a repeat biopsy in order to continue on protocol.

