9. BIOMARKER, CORRELATIVE, AND SPECIAL STUDIES

9.1 Clinical specimens collected

The following clinical specimens will be collected from patients on this study:

- a) Archival tumor tissue if available (paraffin-embedded)
- b) Blood at baseline (for collection of plasma, germline DNA and ctDNA).
- c) Blood at each time of restaging (for collecting ctDNA)
- d) Blood at C1D15, C2D1, C3D1, and at progression (for plasma)
- e) Tumor biopsy material obtained at time of study entry (if accessible disease) – both fresh frozen and formalin-fixed, paraffin-embedded

- f) Tumor biopsy material obtained at time of C2D1 (if accessible disease) – both fresh frozen and formalin-fixed, paraffin-embedded
- g) Blood at time of progression for collection of ctDNA
- h) Stool at baseline, on treatment, toxicity, and EOT/PD

Sample	Type	Visit
Archival Tissue FFPE	Tumor	Screening
Fresh Tissue FFPE and Frozen	Tumor	Screening and Cycle 2 day 1
cfDNA	Blood	Screening, Restaging, and Progression
Plasma for isolation of exosomes	Blood	Screening, C1D15, C2D1, C3D1, and Progression
Germline DNA	Blood	Screening
PBMCs	Blood	Screening, C2D1, C3D1, and Progression
Stool	Stool	Screening, Between C2D1-C3D1, grade ≥ 2 diarrhea (optional), and EOT/PD

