9.7.1.3 Risks of Research Biopsy and Procedures for Minimizing Risk

Potential risks according to site are:

Breast (core biopsy):

- Likely: local discomfort and minor bleeding.
- Less likely: moderate or major bleeding, need for blood transfusion, hospitalization due to bleeding or other complications, infection, pneumothorax, damage to adjacent organs.

Skin/chest wall (punch biopsy):

- Likely: local discomfort and minor bleeding
- Less likely: moderate or major bleeding, or infection

Lymph node, liver, or bone (core needle biopsy):

- Likely: local discomfort and minor bleeding
- Less likely: moderate or major bleeding, need for blood transfusion, hospitalization due to bleeding or other complications, infection, damage to adjacent organs. Additional risks may be present if intravenous conscious sedation is required

Pleural fluid (thoracentesis):

- Likely: local discomfort and minor bleeding
- Less likely: moderate or major bleeding, need for blood transfusion, hospitalization due to bleeding or other complications, infection, pneumothorax, damage to adjacent organs

Ascites fluid (paracentesis):

- Likely: local discomfort and minor bleeding
- Less likely: moderate or major bleeding, need for blood transfusion, hospitalization due to bleeding or other complications, infection, bowel perforation or damage to adjacent organs. In order to minimize the risk of a biopsy, only qualified personnel will perform these procedures.

Prior to the procedure, the physician performing the procedure will discuss the risks with each study participant, answer any questions, and obtain separate procedure consent. Patients will be evaluated for comorbidities or concomitant medications that may increase the risk of potential complications. For biopsies of lesions that are not superficial and clearly palpable, imaging studies such as CT or ultrasound will be used to guide the biopsy in order to minimize the risk of damage to adjacent structures. After lymph node biopsies, patients will be observed a minimum of 2 hours (range 2-4 hours) after the procedure, or according to standard institutional guidelines. After liver biopsies, patients will be observed a minimum of 4 hours (range 4-6 hours) after the procedure, or according to standard institutional guidelines. Less than the goal quantity of tissue is accepted for each type of biopsy, and will be left to the clinical judgment of the physician performing the procedure.

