A portion of the baseline biopsy will have RNA extracted. This RNA will then be subjected to analysis of gene expression by Affymetrix microarray and/or using the Nanostring nCounter platform. Tumors will be classified according to published algorithms to determine their individual TNBC subtype. We expect that the majority (but not all) of the RB-positive tumors will fall into the “Luminal Androgen Receptor” or “Mesenchymal Stem Like” subtypes, and as an exploratory analysis will determine if tumors within this subtype have a higher rate of response to abemaciclib. Additionally, in patients who consent, RNA extracted will be used to quantify the expression of several genes, including (but not limited to) those used to classify tumors into PAM50 subtypes[18], those identifying specific TNBC subtypes [19][8], and those that contribute to a signature of RB proficiency or deficiency. This will allow us to depict the landscape of gene expression for all tumors in this study, and also to determine in an exploratory fashion the correlation (or lack thereof) between RB positivity by IHC and “Rb-proficiency” by gene expression. The Nanostring assay will be performed at the BWH Center for Advanced Molecular Diagnostis (CAMD). Some portion of de-identified patient clinical information will be shared with Nanostring Technologies, with patient permission, in exchange for the kits needed to perform this assay.

Analysis of paired baseline and C2D1 biopsies

- a) Phospho-RB: FFPE tissue from baseline and C2D1 biopsies will be stained for p-RB (ser780) using protocols established at the Brigham and Women’s Hospital. Sections will be scored manually and the percentage of positive tumor cells will be recorded – a minimum of 200 cells will be counted. A tumor H score will be calculated. We will determine whether (i) baseline RB phosphorylation level predicts response to abemaciclib and (ii) whether suppression of RB phosphorylation after commencement of therapy is associated with an increased response rate.

- b) FFPE tissue from baseline and C2D1 biopsies will be stained for proteins involved in the regulation of cell proliferation in the lab of [name], PhD at Dana-Farber Cancer Institute.

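### A patient whose baseline research biopsy gave no usable tumor tissue is still due the cycle 2 day 1 biopsy, although every assay specified for that later tissue is a paired comparison

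*Combined protocol and SAP*

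**What the plan says.** **After an inadequate baseline biopsy.** Section 9.7.1.1 keeps these participants on study: those "in whom inadequate tissue is obtained, are still eligible and are not required to undergo a repeat biopsy in order to enter the study". Section 3.1.17 says that they "are not required to undergo a repeat biopsy in order to continue on protocol".

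**The second biopsy.** After requiring a pre-treatment biopsy where disease can be reached, Section 2.4 continues: "In addition, patients will undergo a second biopsy after completion of 1 cycle (28 days) of abemaciclib therapy". Section 9.1, item (f), lists "Tumor biopsy material obtained at time of C2D1 (if accessible disease", and accessibility is its only condition. The research-biopsy row of the study calendar (Section 10) marks C2D1 without a footnote. Section 9.7.1.1 gives one waiver: "Research biopsies can be waived, with PI approval, in participants who do not have easily accessible disease".

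**What the C2D1 tissue is for.** Section 2.4 states the purpose: "Comparison of RB phosphorylation between baseline and C2D1 biopsies will be used to seek evidence of pharmacodynamic effect". Section 9.7.1.6 lists the assays (p-RB and proliferation proteins, both on FFPE sections) under "Analysis of paired baseline and C2D1 biopsies". Section 13.4 defines phospho-Rb reduction from paired samples and powers the comparison on the number of evaluable pairs.

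**The risk.** For lymph node, liver or bone core biopsy, Section 9.7.1.3 lists among the less likely harms "moderate or major bleeding, need for blood transfusion, hospitalization due to bleeding or other complications", as well as infection and damage to adjacent organs.

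**The concern.** A biopsy done only for research needs a stated scientific return. For the C2D1 biopsy, that return is a change from baseline. Without usable baseline tissue there is no change to measure, yet nothing in the protocol cancels the second procedure or makes it optional. At stake is participant protection: a few people may have an invasive procedure that cannot serve the phospho-Rb objective for which it was planned.

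The protocol already follows this logic for a sample that carries no procedural risk. Under Section 9.8.1, a patient's stool series may stop when the baseline sample is missing, because the analysis depends on it. Elsewhere the protocol limits research biopsies by risk or yield: lung nodules and procedures under general anesthesia are ruled out unless there is a clinical reason, and bone is a last choice. A failed baseline biopsy is the case left uncovered.

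**Working it through.** **1. Is the second biopsy still due?** The relevant provisions, side by side:

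| Provision | Condition | Covers a failed baseline sample? |
|---|---|---|
| 3.1.17 and 9.7.1.1, no repeat needed | Inadequate tissue | Most naturally the baseline attempt only; 9.7.1.1 ties it to study entry |
| 2.4, second biopsy | Accessible disease | No exemption |
| 9.1(f) | Accessible disease | No exemption |
| Section 10 calendar, C2D1 | None shown | No exemption |
| 9.7.1.1, waiver | Disease not easily accessible, with PI approval | Not a stated ground |

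Read together, the second biopsy goes ahead. This rests on the absence of an exemption; no sentence expressly requires it after a failed baseline.

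**2. Can unpaired C2D1 tissue enter a specified analysis?**

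- Section 9.7.1.6 asks two p-RB questions. The first uses the baseline level alone. The second uses suppression after treatment starts, which needs both samples. Neither uses C2D1 alone.
- The proliferation-protein stain is listed under the same paired heading.
- Section 13.4 uses reduction as a yes/no variable from pairs. The exploratory logistic models in that section use quantitative reduction, which also needs the pair.
- Section 2.4 lets archival tissue stand in for a missing pre-treatment biopsy when predictive markers are studied. It does not name archival tissue as a baseline for the p-RB comparison.

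So no specified C2D1 tissue assay can use the sample.

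**3. How many patients?** The inputs, from Sections 13.2 and 13.4, are 37 evaluable patients, 33 evaluable pairs and a 10% failure rate.

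- Check of the stated count: 37 × (1 − 0.10) = 33.3, which matches 33.
- Pairs lost: 37 − 33 = 4 (37 × 0.10 = 3.7).
- If every lost pair is a baseline failure followed by a C2D1 biopsy: about 4.
- If losses split evenly between the two visits (an assumption): about 2.
- If every loss has another cause (biopsy waived, patient off treatment before C2D1, C2D1 sample or assay failure): 0.

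The documents give no baseline failure rate of their own. For scale, an assumed rate of 5% to 20% gives 37 × 0.05 = 1.85 to 37 × 0.20 = 7.4, or about 2 to 7 patients.

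**4. Does dropping these biopsies cost power?** First, the plan's own figure. With 33 pairs and 60% showing reduction, the groups are 20 and 13 (33 × 0.6 = 19.8). The disease control rates are 53.3% and 5%, and 0.6 × 53.3% + 0.4 × 5% = 34.0%, the stated overall rate. Power is the sum of Bin(x; 20, 0.533) × Bin(y; 13, 0.05) over all tables with two-sided Fisher p ≤ 0.05. The result is 85.4%, against a stated 85%. All eight cells of the table in Section 13.4 reproduce within one percentage point.

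A patient without usable baseline tissue adds zero pairs whether or not the second biopsy is done. Pairs stay at 33 and power at 85.4%.

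**The case against.** **The tissue is not useless.** Section 12.3 collects tissue for correlative endpoints and possible future work, Section 9.7.1.5 makes specimens available to other investigators, and Section 13.6.2 includes everyone with an evaluable specimen in biomarker analyses. The tumor-tissue objective in Section 1.4 has no pairing condition. This stands. A reader might infer that an unpaired C2D1 sample yields nothing analyzable; the documents do not support that. But these provisions are generic, and none names an analysis of unpaired C2D1 tissue.

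**The obligation is inferred from silence.** The wording in Section 3.1.17 about continuing on protocol could be stretched to cover the second biopsy. A failed attempt that reveals poor access might fall under the existing waiver. No provision makes continued treatment depend on the C2D1 biopsy, and the consent pages are not available here. This is a fair caution. It shows that the text needs a sentence, not that it already has one.

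**Inadequate does not mean unusable.** The term is undefined. Five cores are the ideal, and a short sample may still give the 200 cells that p-RB scoring needs. This stands, so the point is confined to patients with no usable baseline tissue.

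**An FFPE-only condition would go too far.** Two of five baseline cores and three of five C2D1 cores are frozen, and Section 9.5 describes germline sequencing as a control for paired tumor biopsies. A frozen pair might still be usable. This stands and shapes the fix.

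**Safeguards exist.** Section 9.7.1.3 requires a risk discussion, separate procedure consent and a review of comorbidities and concomitant medication. A blood count is scheduled on C2D1. These reduce the risk but supply no scientific return.

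**Conclusion.** The point holds in a limited form. As written, a patient with accessible disease and no usable baseline tumor tissue stays on study and is still due the C2D1 research biopsy. That patient cannot contribute to the paired analyses, which are the only ones specified for C2D1 tissue. What remains is generic banking or future research use.

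The number affected is between 0 and about 4 of 37 if the 10% overall pair-failure rate holds. A reader might take that 10% as the baseline failure rate; Section 13.4 does not say so.

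The conclusion assumes that the no-repeat wording refers to the baseline attempt and that archival tissue is not meant as the p-RB baseline. It is about participant protection and clarity. No stated figure is wrong, and neither the primary endpoint nor the power of the phospho-Rb comparison is affected.

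**What to change.** State in Section 9.7.1.1, in Section 9.1(f) and in a calendar footnote that the C2D1 research biopsy is done only in patients whose baseline biopsy yielded tumor tissue usable for at least one planned paired assay, whether FFPE or frozen, and that this is checked before C2D1. This brings the biopsy into line with the stool rule in Section 9.8.1. The baseline biopsy precedes cycle 1 day 1, so at least one 28-day cycle is available for the check. For comparison, Section 9.2.1 expects about 7 to 14 days for the archival RB stain.

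If the sponsor means archival FFPE to serve as the p-RB baseline, or wants unpaired C2D1 tissue, the protocol should say so and name the analysis. Either answer closes the gap.

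The cost is a sentence in two sections, one footnote and a check of tissue already collected. The downside is that a few unpaired on-treatment samples would not be banked. No evaluable pair is lost.
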